the participant may have. A HIPAA Authorization form will also be provided to the participant. The provision of consent on both forms is necessary for further study participation. If consent is provided, demographic information will also be collected at this time. Participants will also be asked to provide a home address so coordinators can provide an estimation of transportation costs that can be reimbursed in future visits. Then, the clinical research coordinator will measure participant blood pressure three times with one-minute intervals between measurements. Measurements will be made using an Omron HEM-907XL device. These measurements will be used to ensure that participants are not in violation of the study's eligibility criteria concerning hypertension. The coordinator will also ensure that participants have readily available veins for blood draws during the Laboratory Visit. A copy of blood pressure readings will be provided to participants. Next, the "ISQ: Psychometric Evaluation" will be administered as a short survey to ensure that participants do not experience insomnia, another condition precluding participation in the study. If the participant does not meet eligibility criteria for either blood pressure or insomnia, then the participant is compensated and the visit will end.

If the participant remains eligible, then the "Life Events Checklist" and "PTSD Checklist" will be provided separate from the other measures to ensure that the completion of these two questionnaires does not alter stress felt during the Laboratory Visit. Stress- and demographic-related measures will be presented to participants using Qualtrics opened on a provided laptop, and the insomnia survey will be administered as a paper form. The participant's weight, height, hip and waist circumference, gender, age, normal activity levels, and dietary limitations will then be recorded on a Bionutrition Center form. In addition, a list of foods provided by the Bionutrition Center will be provided and the participant asked whether they agree to eat all of the foods on the checklist. This information will be recorded for research use and forwarded to the Bionutrition Center to prepare the meals and snacks that will be consumed in the three days prior to the Laboratory Visit.

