
Risk of Breach of Confidentiality

A risk of taking part in this study is the possibility of a loss of confidentiality. Loss of confidentiality includes having personal information shared with someone who is not supposed to see or know about your information. The study team plans to protect participant confidentiality.

6. Benefits

Participants will not receive personal (direct) benefit from taking part in this research study. However, the information collected from this research may help others in the future.

7. Alternatives

Participants may choose not to take part in this research study.

8. Data and Safety Monitoring

The research team will monitor the study to prevent any risks or dangers that may occur and will appropriately report any adverse events according to IRB policy.

If a participant feels upset or experiences emotional distress, a member of the research team will be available to talk to them and discuss appropriate care. He/she will be offered a period of rest from study activities, and he/she will also be reminded that participation may be discontinued willingly at any time. Further, should any psychological issues arise, clinical psychologists on staff at the [name] Hypertension Lab (BB-210 and Tower 1) will also be available to evaluate the participant. If the participant needs further attention, he/she will be escorted to the emergency room for further evaluation. If there is no immediate risk, the participant will remain until the end of the study visit and be discharged. Participants will then be referred to their primary care doctor and as appropriate, the Columbia University Psychiatry Referral Line for further management.

Participants will be provided with copies of their own blood pressure and apnea-hypopnea index (AHI) measurements after this data is collected at the Enrollment Visit or during the following night.

The average blood pressure reading will be accompanied by a group of recommendations from the American Heart Association regarding actions that should be taken for abnormal values. If the average BP (systole ranges/diastole ranges) is high normal, or 120-139/80-90 mmHg, it will be recommended that participants ask a physician about lifestyle changes and be rechecked within a year. If the average

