BP is mildly elevated, or 140-159/90-99 mmHg, it will be recommended that participants meet with their doctors to confirm this reading and receive instruction within a month. If the average BP is high, or 160-179/100-109 mmHg, it will be recommended that participants meet with their doctors for a follow-up within a week. If the average BP is very high, or 180-209/110-119 mmHg, it will be recommended that participants meet with their doctors for a follow-up within a week. If the average BP is very high, or 180-209/110-119 mmHg, it will be recommended that participants meet with their doctors for a follow-up within a week. If the average BP is equal to or greater than 210/120, participants will be escorted to the emergency room for immediate care.

The measured AHI value will be accompanied by a list of AHI ranges that correspond to mild, moderate, or severe sleep apnea. If the participant's measured AHI falls outside of the normal range, the participant will be informed that such a diagnosis warrants further evaluation and possible treatment by a physician, and the form itself will reiterate that they inform their regular physician of these results and ask for further guidance. If the participant does not have a primary care physician, then research staff will offer to refer the participant to a primary care physician at Columbia University Medical Center/Columbia Doctors for follow-up.

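### Protocol Section 8 prints diastolic 90 in two adjacent blood pressure bands and gives no rule for systolic and diastolic values that fall in different bands

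*Protocol*

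**What the plan says.** At the Enrollment Visit (Protocol Section 3a) the coordinator will "measure participant blood pressure three times with one-minute intervals between measurements". Section 8 then says: "The average blood pressure reading will be accompanied by a group of recommendations". Two adjacent bands are at issue:

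- The lower band is "high normal, or 120-139/80-90 mmHg". The advice is to "ask a physician about lifestyle changes and be rechecked within a year".
- The next band applies if the average "BP is mildly elevated, or 140-159/90-99 mmHg". The advice is to "meet with their doctors to confirm this reading and receive instruction within a month".

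The higher bands are 160-179/100-109, 180-209/110-119, and 210/120 or above. The only guide to the notation is the parenthesis in "If the average BP (systole ranges/diastole ranges) is high normal", which says which number is systolic and which is diastolic. Neither the protocol nor the SAP says whether both numbers must fall in a band, whether one is enough, or whether the more urgent category governs.

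**The concern.** The bands decide how soon a person is told to see a doctor. A diastolic average of 90 belongs to a band with a one-year horizon and also to a band with a one-month horizon. With no assignment rule, two coordinators could give different advice for the same reading, and the most literal reading of 130/90 gives the less urgent advice. The missing rule also matters away from 90, wherever the two numbers point to different bands. What is at stake is the consistency of safety feedback to participants, not the study's inference.

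**Working it through.** The plan has no figure of its own to reproduce here. The check is a classification exercise on the limits printed in Section 8, taken as inclusive whole numbers.

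**Step 1: the boundaries.** Five ordered bands give four systolic and four diastolic boundaries.

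- Systolic: 139/140, 159/160, 179/180, 209/210. No shared value.
- Diastolic: 90/90, 99/100, 109/110, 119/120. One shared value, 90.

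So 1 of 8 boundaries overlaps. The other 7 are clean for whole numbers, which suggests a slip of one digit.

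**Step 2: readings under the printed text.** "One year" and "one month" are shown below without quotation as the advice for the lower and upper of the two bands.

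| Average | Both numbers must match | Either number suffices | More urgent governs (not stated) |
|---|---|---|---|
| 130/90 | one year | one year and one month | one month |
| 145/90 | one month | one year and one month | one month |
| 115/90 | no band | one year and one month | one month |
| 130/95 | no band | one year and one month | one month |
| 150/85 | no band | one year and one month | one month |

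**Step 3: what the overlap itself causes.** Replace 80-90 by 80-89 and change nothing else.

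| Average | Both numbers must match | Either number suffices | More urgent governs |
|---|---|---|---|
| 130/90 | no band | one year and one month | one month |
| 145/90 | one month | one month | one month |
| 115/90 | no band | one month | one month |
| 130/95 | no band | one year and one month | one month |
| 150/85 | no band | one year and one month | one month |

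Under the either-number reading, the overlap is what produces the second recommendation at 145/90 and 115/90. At 130/90 it is not: 130 and 90 lie in different bands with or without it. Under the paired reading, the overlap is what puts 130/90 in high normal. Correcting the digit alone leaves that reading with no band.

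**Step 4: rounding.** The mean of three whole-number readings ends in .00, .33 or .67. If it is not rounded, two values fall between bands at each clean boundary: 2 x 7 = 14 as printed, and 2 x 8 = 16 once 80-89 is used (89.33 and 89.67 are added). Rounding to whole mmHg leaves none, and a mean of three whole numbers never ends in .50, so there are no ties.

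**The case against.** The strongest reply is that this is a drafting slip with little practical consequence. A strict paired reading is unlikely to be intended, since it leaves 130/95 and 150/85 with no advice. Under the either-number reading the two recommendations are compatible, because someone who sees a doctor within a month can also discuss lifestyle and be rechecked within the year. Staff may simply apply the more urgent category. The participant form and the external recommendations that Section 8 draws on are not in the documents, and either may print 80-89 or carry a rule. There are other safeguards: Section 3a says "A copy of blood pressure readings will be provided to participants", and Section 3c offers ambulatory results and, for those without a provider, a primary-care referral after completion.

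Much of this stands, and it limits the point to a minor one. It does not remove it: the protocol gives two time limits for one diastolic value, and the rule that would settle the matter is not written down.

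A reader might infer more than the text supports:

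- **That 130/90 must get either both recommendations or only the less urgent one.** If the more urgent category governs, it gets the one-month advice. That rule is not stated, but neither is it excluded.
- **That the overlap is why 130/90 could get two recommendations.** Step 3 shows otherwise.
- **That the number affected can be capped as a share of the 211 participants.** Advice goes to everyone measured at the Enrollment Visit, including people later excluded. The blood pressure eligibility limit is not given, and a count at diastolic 90 alone would miss discordant pairs such as 130/95.
- **That someone has received wrong advice.** Without the form, the documents cannot show this.

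**Conclusion.** The point holds as a minor inconsistency in participant safety feedback. Two facts rest on the text alone: diastolic 90 is printed in two adjacent bands, and no rule assigns discordant values. The size of the discrepancy for an affected person is a month versus a year, or no band at all for some discordant readings under the literal paired reading. The number of people affected is unknown, because the documents give neither the blood pressure distribution nor the number attending the Enrollment Visit. The rounding remark assumes that the device reports whole mmHg and that averages are otherwise left unrounded; the documents are silent on both. Endpoints, analysis and sample size do not depend on these bands.

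**What to change.** In Protocol Section 8, change the high-normal range to 120-139/80-89. Add one sentence: averages are rounded to the nearest whole mmHg, and when systolic and diastolic values fall in different categories the more urgent one applies. With both changes, 130/90, 115/90, 145/90, 130/95 and 150/85 each get the one-month advice and nothing else, and the same sentence settles discordant readings in the higher bands. The digit change should not be made alone, for the reasons in Steps 3 and 4. Check that the participant form prints the same limits and rule. The sentence on the 180-209/110-119 band is printed twice and can be cut to one in the same edit.

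The cost is one digit, one sentence and a form check. Data collection and analysis do not change.

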Stress, Salt Excretion, and Nighttime Blood Pressure NCT03636490 Last IRB approval date: 01/07/2025

Statistical analyses

Participant characteristics for the analytic sample were summarized as mean and standard deviation (SD) for continuous variables and percentages for categorical variables. As a fidelity check of the mental stress tasks, we examined the pre-/post- change in VAS stress rating in the laboratory session.

To determine the association between urinary sodium excretion rate with stress in the laboratory and awake-to-asleep ratio of urinary sodium excretion over a 24-hour period, standard regression analysis as used in unadjusted and adjusted models. We have *a priori* selected the following covariates for adjustment in a multiple regression model: age, sex, race, and ethnicity (non-Hispanic whites, non-Hispanic blacks, Hispanics, and other), and body mass index. Age, sex, and race/ethnicity are standard covariates in studies of hypertension given their well-known associations with BP. Body mass index was included as a covariate since it is associated with both lower stress-induced sodium excretion and lower daytime-to-nighttime ratio of urinary sodium excretion rate. Prior data has indicated that higher clinic SBP, higher clinic DBP and parental history of hypertension are associated with lower stress-induced sodium excretion. Further, blood glucose and 24-hour creatinine clearance are associated with lower daytime-tonighttime ratio of urinary sodium excretion rate. Each of these were evaluated as candidate covariates by selecting those that are associated with awake-to-sleep ratio of urinary sodium excretion rate at p<0.10.

To determine the association between awake-to-asleep ratio of urinary sodium excretion and SBP dipping over a 24-hour period, standard regression analysis was also used in unadjusted and

adjusted models. The *a priori* covariates that were included in adjusted models are age, sex, race, ethnicity, body mass index, current smoking, alcohol use (none, moderate, heavy), blood glucose, 24-hour sodium excretion, 24-hour potassium excretion, 24-hour creatinine clearance, and FENa. In addition to age, sex, and race/ethnicity, the other measures were chosen as covariates as prior studies indicate they may confound the association between the diurnal pattern of sodium excretion and the diurnal pattern of BP. These analyses were repeated by replacing SBP dipping with DBP dipping.

In secondary analyses, we also examined whether the association between urinary sodium excretion rate with stress in the laboratory and awake-to-asleep ratio of urinary sodium excretion over a 24-hour period was modified by EMA ratings of perceived stress. Controlling for each EMA rating and change in urinary sodium excretion rate with stress, we tested their multiplicative interaction term in a fully adjusted model. A positive interaction effect would suggest that the association between urinary sodium excretion rate with stress in the laboratory and awake-to-asleep ratio of urinary sodium excretion over a 24-hour period is stronger among those who experience higher stress during the awake period of monitoring. The analyses were repeated for each EMA rating of negative affect.

A p value of <0.05 was considered statistically significant.

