Exposure to an acute stressor using a mental stress task normally increases urinary sodium excretion in the laboratory setting. However, there is substantial variability between individuals in the degree of stress-induced sodium excretion. Individuals with lower stress-induced sodium excretion who experience psychological stress during the daytime may exhibit a shift of urinary sodium excretion from the daytime to nighttime periods due to an inability to excrete additional sodium during the daytime. This abnormal *diurnal* pattern of urinary sodium excretion may, in turn, be associated with a smaller decline in BP from the daytime to nighttime periods, leading to reduced BP dipping and elevated nighttime BP. The overall goal of the proposed study is to examine the associations between psychological stress, the *diurnal* pattern of sodium excretion, and the *diurnal* pattern of BP. The aims of the study are:

Primary Aim 1: To examine the association between urinary sodium excretion after provoked psychological stress and the diurnal pattern of sodium excretion.

Primary Aim 2: To examine the association between the diurnal pattern of sodium excretion and the diurnal pattern of BP.

Two secondary or exploratory aims that will also be investigated:

Secondary Aim: To examine whether the association between urinary sodium excretion after provoked stress and the *diurnal* pattern of sodium excretion is modified by ecological momentary levels of perceived stress, experienced during the daytime period.

Exploratory Aim: To determine the sociodemographic, behavioral, and psychological traits, chronic stress, and biological stress-related factors that are associated with lower stress-induced sodium excretion. Identification of these factors will help determine who is at risk for having a differential sodium excretion response to psychological stress.

2. Study Design

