Primary Aim 1: Standard regression analysis will be used. We will estimate the unadjusted relation of awake-to-sleep ratio of urinary sodium excretion rate to change in urinary sodium excretion rate with stress. Next, we have a priori selected the following covariates for adjustment in a multiple regression model: age, sex, race/ethnicity (non-Hispanic whites, non-Hispanic blacks, Hispanics, and other), and body mass index. Age, sex, and race/ethnicity are standard covariates in studies of hypertension given their well-known associations with BP. Body mass index is included as a covariate since it is associated with both lower stress-induced sodium excretion and lower day-to-night ratio of urinary sodium excretion rate. The statistical significance of the coefficient for the change in urinary sodium excretion rate with stress in this adjusted model will constitute the primary test of the hypothesis. Sensitivity analyses will be performed to assess whether the strength of the association changes when additional covariates are included. Higher clinic SBP/DBP and parental history of hypertension are associated with lower stress-induced sodium excretion. Fasting blood glucose and 24-hour creatinine clearance are associated with lower daytime-to-nighttime ratio of urinary sodium excretion rate. Each of these will be evaluated as candidate covariates by selecting those that are associated with the outcome (awake-tosleep ratio of urinary sodium excretion rate) at p<0.10. Finally, secondary analyses will use generalized additive models (GAM) to explore potential non-linearity of the relationship, using PROC GAM in SAS.

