Primary Aim 2: The same approach for Hypothesis 1 will be used for the analysis of this hypothesis. SBP dipping and DBP dipping will be the primary and secondary outcomes, respectively. The *a priori* covariates that will be included in adjusted models are: age, sex, race/ethnicity, body mass index, 24-hour sodium excretion, 24-hour potassium excretion, 24-hour creatinine clearance, FENa, current smoking, alcohol consumption, and fasting blood glucose. In addition to age, sex, and race/ethnicity (which were chosen because they are standard covariates in hypertension studies), the other measures were chosen as covariates as they may confound the association between the *diurnal* pattern of sodium excretion and the *diurnal* pattern of BP. Sensitivity analyses will be performed after additional covariates are included in the adjusted model. Prior studies have suggested that physical activity and fasting glucose are associated with the diurnal pattern of BP. Each of these measures will be evaluated as candidate covariates using the same approach described above for Primary Aim 1.

Sample Size and Minimum Detectable Effect Sizes for Primary Aims: The sample size for this study was selected to ensure 80% power to detect a bivariate/partial correlation between the primary predictor and outcome of r=0.20 or greater; this is conservative, but consistent with our preliminary data in which the correlation between the change in urinary sodium excretion rate with stress and awake-to-sleep

ratio of urinary sodium excretion rate (Primary Aim 1) was 0.25, and the correlation of awake-to-sleep ratio of urinary sodium excretion rate and SBP dipping (Primary Aim 2) was 0.30. The minimum sample size required to detect this effect size with power 80% is 194 with valid data for the three primary measures (change in urinary sodium excretion rate with stress, awake-to-sleep ratio of urinary sodium excretion, and SBP dipping). We are targeting a final minimum sample size with complete data of 200.

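### Does the SAP's short account of the EMA interaction tests give the negative-affect results too much weight, or misread a positive interaction?

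*SAP*

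**What the plan says.** The Secondary Aim (protocol section 1) asks whether the association between stress-induced sodium excretion and the diurnal sodium pattern "is modified by ecological momentary levels of perceived stress, experienced during the daytime period". Protocol section 4, Secondary Aim, defines the moderator as mean perceived stress over the EMA reports. It reads a positive interaction in a named direction: the expected pattern, in which people who excrete less sodium under stress also have a lower day-to-night ratio, is more marked on high-stress days. Section 4, Additional Exploratory Analyses, repeats this for four negative affects and for their average.

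The SAP's paragraph on secondary analyses opens with perceived stress as the modifier. It describes the model as "Controlling for each EMA rating and change in urinary sodium excretion rate with stress", with the product term tested in the fully adjusted model. It says a positive interaction would suggest that the association "is stronger among those who experience higher stress during the awake period of monitoring", and closes with "The analyses were repeated for each EMA rating of negative affect". One threshold covers the whole SAP: "A p value of <0.05 was considered statistically significant".

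**The concern.** Read alone, the SAP paragraph seems to lose three things.

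- **Rank.** The affect repeats sit in the secondary paragraph, under the same 0.05 threshold and without the word exploratory. The phrase about each EMA rating seems to put all moderators on one footing. One nominal affect result could then be given the weight of the Secondary Aim.
- **Composite.** The protocol's composite is not mentioned. Because the SAP is in the past tense, a reader may wonder whether it was run.
- **Direction.** The SAP says the association is stronger but not which association. If the slope were negative, a positive interaction would shrink it towards zero or reverse it, and the word would mislead.

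**Working it through.** **1. The plan's own figure.** The only sample-size calculation is for a "bivariate/partial correlation between the primary predictor and outcome of r=0.20 or greater". By Fisher's z, N = ((1.960 + 0.842)/atanh(0.20))² + 3 = 193.97, so 194 as stated. A one-sided 0.05 would give 153.4, so 154. The documents do not state sidedness, but the figure implies two-sided tests. Power at the target of 200 is 0.812. Nothing here concerns the interactions.

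**2. Rank, with the two documents side by side.**

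| Item | Protocol | SAP |
|---|---|---|
| Perceived stress | Secondary Aim | Named alone in the lead sentence |
| Four affects | Exploratory repeats | Repeats, in a separate closing sentence |
| Composite of four | Exploratory | Not mentioned |
| Multiplicity rule for these tests | None | None |

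The order of lead test and repeats survives; only the label is missing. Nor does the SAP's phrase *secondary analyses* show a promotion. The protocol uses it loosely too: under Primary Aim 1, "secondary analyses will use generalized additive models (GAM) to explore potential non-linearity of the relationship". The false discovery rate in the protocol belongs to the Exploratory Aim and is not extended to these interactions, so the SAP dropped no adjustment.

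**3. Multiplicity.** For four independent tests at 0.05, the chance of at least one false positive is 1 − 0.95⁴ = 0.185. At assumed equal correlations of 0.3, 0.5, 0.7 and 0.9, simulation gives 0.174, 0.156, 0.131 and 0.093. Adding the composite gives 0.203 at correlation 0 and 0.158 at 0.5. The same tests at the same threshold stand in the protocol, and a label changes none of these rates.

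**4. Direction.** Let M be the centred, standardised EMA rating. The Aim 1 slope at M is b1 + b3·M.

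- *Signed reading (the protocol's).* If b3 > 0, the slope rises with M whatever the sign of b1. The lower-with-lower tendency is always greater at higher stress, so the sentence is right.
- *Unsigned reading (size of the slope).* (b1 + b3)² − (b1 − b3)² = 4·b1·b3. With b3 > 0, the slope at +1 SD is larger in size than at −1 SD exactly when b1 > 0. With an illustrative b3 = 0.10, b1 = 0.25 gives 0.35 at +1 SD (stronger), and b1 = −0.25 gives −0.15 (weaker).

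**5. How often the unsigned reading would mislead.** The sentence is used only when the interaction is positive and, in practice, significant. A misreading therefore needs that and a negative estimated b1. Take n = 200, standardised variables, predictor and moderator independent, and SE = √((1 − b1²)/196).

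| True b1 | Source | P(estimated b1 < 0) = Φ(−b1/SE) |
|---|---|---|
| 0.25 | pilot | 0.00015 |
| 0.20 | planned | 0.0021 |
| 0.10 | assumed | 0.080 |
| 0.05 | assumed | 0.242 |
| 0 | assumed | 0.50 |

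The pilot value is the protocol's awake-to-sleep "ratio of urinary sodium excretion rate (Primary Aim 1) was 0.25". The right-hand column approximates the chance of a misreading *given* a significant positive interaction. The joint chance multiplies it by the chance of such an interaction:

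- b1 = 0, no interaction: 0.50 × 0.025 = 0.0125, about 1.3%.
- b1 = 0.10, assumed interaction 0.10 (power about 0.30): 0.080 × 0.30 = 0.024; simulation gives about 2.6%.
- b1 = 0.20: at most 0.0021, about 0.2%, even if the interaction were certain to be significant.

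**6. Slopes that change sign.** Among significant positive interactions, the estimated slopes at −1 SD and +1 SD have opposite signs in 18% to 71% of simulated cases at b1 = 0.25, and in 39% to 86% at b1 = 0.20, for assumed interactions of 0.10 to 0.30. The documents give no interaction size. The upper ends are built in: at an interaction of 0.30 the true slope at −1 SD is already 0.25 − 0.30 = −0.05 or 0.20 − 0.30 = −0.10. Where the slope at the mean is positive, calling the association stronger at high stress is still correct.

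**The case for a change.** The best case for a change is that it is cheap. One word would label the affect repeats, one clause would account for the composite, and one phrase would restore the direction. Slopes at the mean and one SD either side, with 95% confidence intervals, come from models already fitted and would show any reversal. If Aim 1 turned out null, the chance of a misreading given a significant positive interaction would be 50%, which is not small.

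The three omissions are real, and tidy reporting would repair them. But each is answered in the protocol that the SAP accompanies. The composite is not singled out: this short SAP also leaves out the generalized additive models, the sleep blood pressure outcomes, the sex and race/ethnicity interactions and the Exploratory Aim. The 50% figure applies only after a significant interaction has appeared. With no true interaction, a significant positive one appears 2.5% of the time. The Aim 1 coefficient is itself the primary result, so its sign would be in view. Slopes with intervals are sensible follow-up reporting, but they add to both documents and correct no rule in either.

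**Conclusion.** No change to the plan is called for. The SAP abbreviates the protocol on rank, composite and direction, and an analyst holding both documents would fill the gaps as the protocol directs. A label would alter no test, threshold or error rate. On the protocol's signed reading the sentence about a positive interaction is always right. On the unsigned reading it misleads with a joint chance of about 0.2% or less at the planned slope, about 1.3% with no slope and no interaction, and about 2.6% at an assumed slope and interaction of 0.10 each.

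These figures assume n = 200, two-sided tests, standardised variables, and a predictor and moderator that are independent; interaction sizes and correlations between affect tests are assumptions. The primary tests and the sample size of 194 are unaffected. Carrying the protocol's label and direction into the report, and saying whether the composite was run, is an editorial courtesy.
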